6.4 Radiotherapy

For a comprehensive and step-by-step approach to the implementation of the preoperative radiotherapy procedure, trial participants are referred to the Radiotherapy Quality Assurance (RTQA) Guidelines. These guidelines provide a detailed explanation and practical instructions for each step of the process, ensuring standardized and quality-assured delivery of pre- and postoperative radiotherapy across all trial sites.

Patients in the experimental arm receive preoperative radiotherapy, starting with whole breast radiotherapy (5x 2.7 Gy to 40.5 Gy +/- Boost RT), preferably 2-3 weeks after the last application of neoadjuvant chemotherapy (NACT). Regional lymph node radiotherapy may be indicated depending on initial findings before NACT and targeted therapy (5x 2.7 Gy to 40.5 Gy). Specific conditions such as central or medial tumor location, ER/PR negative tumor, cT3 or cT4 tumor, cN2 status, inflammatory tumors, or enlarged lymph nodes in the internal mammary chain would necessitate internal mammary chain lymph node irradiation. However, this is not indicated for left-sided cancers treated with trastuzumab +/- pertuzumab or in the presence of relevant cardiac comorbidity. The technique for treatment involves using 3D, IMRT, and VMAT-Planning based on individual CT-slices, with a preference for deep inspiration breath-hold techniques in left-sided breast cancer. The dose planning must follow the ICRU 50, 62, and 83 guidelines. In terms of target volumes and safety margins, CTVs need to be adjusted for locally advanced disease (e.g., T4 or N2/3 disease) to ensure all macroscopic tumor tissue is covered with at least a 5mm safety margin. In cases where clinical complete remission is achieved during the initial therapy and no boost is applied, but histological evidence of tumor cells is subsequently detected following complete resection, the administration of boost after surgery becomes uncertain and is generally not recommended. The treatment protocol allows for the possible inclusion of axillary lymph node irradiation, though caution is advised to prevent lymphedema.

For patients with initially negative clinical lymph node (cN0) and neoadjuvant therapy-induced negative pathologic lymph node (ycN0) status on biopsy but found to have histologically confirmed lymph node metastases at surgery, postoperative radiotherapy of the lymph node regions is recommended. Throughout all of this, cumulative toxicities and dose limits of organs

should be considered and adhered to, with efforts to minimize anatomical shifts between the two planning CTs. Patients should be adequately informed about potential for increased cumulative toxicity.

In the experimental arm, the center decides whether to administer a boost in the situation of complete remission in imaging after neoadjuvant chemotherapy (center's decision).

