4.6 Risk-benefit analysis

Preoperative radiotherapy after neoadjuvant chemotherapy +/- targeted therapy is expected to improve locoregional tumor control, progression free, distant metastasis free, and overall survival compared to postoperative standard radiotherapy. Results of randomized trials are not available. Results from the SEER Database indicate an improvement of progression free survival for breast cancer patients, who had received preoperative radiotherapy [6]. Indirect comparison suggests an approximately 20% higher rate of pathologically complete remission. A systemic effect of preoperative radiotherapy on subclinical distant metastases is presumed to be initiated by an immunogenic tumor cell death after radiotherapy. While in postoperative radiotherapy, little interaction with malignant cells in this regard can be expected, preoperative radiotherapy obviously has a higher potential. Another benefit for patients from preoperative radiotherapy is the expectation that cosmetic results and long-term toxicity are improved. In case of immediate breast reconstruction with autologous tissue, the transferred tissue will not receive radiotherapy and will show less shrinkage. The breast tissue in the region of the primary tumor receives the highest radiation dose (boost) and is responsible as a relevant risk factor for fibrosis and deformation of the irradiated breast. After preoperative radiotherapy, most tissue of this highly irradiated boost volume will be removed during surgery. Less fibrosis and deformation are therefore likely. Furthermore, a considerable part of the irradiated tissue will be removed at surgery and is no longer prone for the development of second cancers.

A small part of patients will have cT1/T2 cN0 M0 breast cancer with unfavorable biology. If these patients were surgically treated with mastectomy after neoadjuvant systemic therapy, postoperative radiotherapy is not indicated according to AGO guidelines, unless tumor progression is observed during neoadjuvant treatment. However, mastectomy in patients with cT1/T2 tumors is usually not indicated.

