5.1 Inclusion Criteria

- 1) Histologically proven invasive, unilateral breast cancer
- 2) Indication for neoadjuvant chemotherapy (+/- antibody treatment or other targeted therapies) in accordance with national and international guidelines
- 3) Indication for radiotherapy
- 4) Female
- 5) Informed consent for the trial signed by the patient
- 6) T2-T4a-d (d: max. 1 cm inflammation)
- 7) T1 a-c, if G3, triple negative, HER2- positive, or cN+/pN+
- 8) Hormone receptor and HER2 status: no restrictions
- 9) All grades G1-G3
- 10) Age ≥ 18 years at the time of randomisation
- 11) status ≤ 2
- 12) No pre-existing conditions that forbid therapy
- 13) Signed consent form regarding registration, randomisation, collecting, and saving of personal data.

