6.4.2 Whole Breast Radiotherapy (WBRT)

In the experimental arm, WBRT should preferably begin 2-4 weeks after the last application of NACT. In case of persistent toxicity that is regarded critical for radiotherapy, up to 6 weeks are allowed. Surgery should be performed after disappearance of the acute radiation induced erythema, preferably 3-6 weeks after completion of pre-operative radiotherapy. In the standard arm, post-operative WBRT should start 3-6 (up to 8) weeks after surgery.

6.4.3 Indication for breast/chest wall and regional lymph node irradiation:

Experimental arm (preoperative radiotherapy)

Preoperative radiotherapy Arm

- all patients receive whole breast radiotherapy (5x 2.7 Gy to 40.5 Gy +/- Boost RT)
- indication for regional lymph node radiotherapy depends on the initial findings before the start of the NACT +/ targeted therapy (5x 2.7 Gy to 40.5 Gy)

Lymph node region	indicated, if initially
Level I*- IV	cN+
Internal mammary chain LN**	cN+ and >=1 of the following factors

1) Central or medial tumor location

- 2) ER/PR negative tumor
- 3) cT3 tumor
- 4) cT4 tumor
- 5) cN2
- 6) inflammatory tumors
- 7) enlarged lymph nodes in the internal mammary chain

* Subtotal RT of Level I- II (see CTV definitions)

** No Internal mammary chain radiotherapy for left sided cancers treated with trastuzumab +/- pertuzumab and/or relevant cardiac comorbidity

Note: indications depend on the pretherapeutic findings irrespective of response to neoadjuvant systemic therapy

* Limited radiotherapy of Level I+II (see CTV definition)

** No IMC radiotherapy for left sided cancers treated in case of trastuzumab+/- pertuzumab or relevant cardiac comorbidity

Standard arm (postoperative radiotherapy):

The indication for whole breast / chest wall, for regional lymph nodes and boost radiotherapy should be administered according to the current recommendations of the AGO guideline.

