6.4.6 Target volumes and safety margins (CTV and PTV)

CTV definition in both arms of the trial should follow the ESTRO guidelines for early breast cancer [49]; however, in case of locally advanced disease (e.g. T4 or N2/3 disease), CTVs need to be adjusted to ensure that all macroscopic tumor tissue is encompassed with at least a 5 mm safety margin.

Experimental arm (preoperative radiotherapy)

CTVb_low = total breast (excluding 5 mm below the skin) including the initial tumor volume + 5mm [+ 2cm skin in case of inflammatory cancer]
(Anatomically adjusted)

GTVp = primary tumor at the time of radiotherapy.

For CR = boost or no boost (GTVp) is indicated (as decided by the local institution)

Based on the presently available evidence, the clinical significance of administering a boost in the neoadjuvant radiotherapy setting subsequent to achieving complete remission via neoadjuvant chemotherapy remains uncertain. Consequently, a universal recommendation cannot be made, as it is contingent upon the cumulative experiences and expertise of the treating institution. In the context of this study, the participating study site will establish, at the outset, whether a boost will be implemented in this particular scenario. Following this determination, all patients within the given study site will receive treatment in accordance with the predetermined local decision.

In cases where clinical complete remission is achieved during the initial therapy and no boost is applied but histological evidence of tumor cells is subsequently detected following complete resection, the decision regarding boost administration after surgery becomes uncertain. The value of a boost in this specific situation, along with the radiobiological concerns associated with a prolonged treatment interruption, raises doubts about its role. Therefore, based on the available scientific evidence, it is not recommended to include boost administration in the protocol for these cases.

GTVn = marked + enlarged LK at time of radiotherapy

CTVp_high = GTVp + 0.5cm

(Anatomically adjusted)

CTVn = GTVn + 5mm + Level 1-2 (upper border 1 cm below V. axillares) + Level 3-4 + IMC (if indicated according to protocol)

PTVb_low = **CTVb_low** + 5-8 mm

PTVb_high = **CTVp_high** + 5-8 mm

PTVn = **CTVn** + 5-8 mm

No Gaps between **PTVb_low** and **PTVn** allowed

PTV concept in case of axillary lymph node irradiation

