In axillary lymph node irradiation, the PTV should be limited below the level of the axillary vein at a distance of 0.5cm to prevent lymphedema, unless positive lymph nodes including a 0.5cm CTV margin, cross this virtual boundary. Positive lymph nodes should be contoured with a margin of 0.5 cm. If a lymph node including a safety margin extends outside the PTV this volume should be added to the CTV.

Patients with initially negative clinical lymph node (cN0) and neoadjuvant therapy-induced negative pathologic lymph node (ycN0) status on biopsy, but subsequently found to have histologically confirmed lymph node metastases at the time of surgery, who did not receive radiation to the axillary lymph node (ALN) region in the experimental arm are recommended for postoperative radiotherapy of the lymph node regions with field margin connection. It is important to note that cumulative toxicities should be considered in both treatment plans, and the cumulative dose limits of organs should be adhered to without accounting for potential recoveries (as significant recovery within such a short timeframe is unlikely). Efforts should be made to minimize anatomical shifts between the two planning CTs to minimize additional uncertainties. The patient should be adequately informed about the potential for increased cumulative toxicity. In these cases, it is advisable to involve the study leadership closely in the planning and implementation of the therapy.

Standard Arm (postoperative radiotherapy)

In case of breast conserving surgery:

CTVb_low = total breast (excluding 5 mm below the skin) including the initial tumor volume + 5mm [+ 2cm skin in case of inflammatory cancer]
(Anatomically adjusted)

GTVp = tumor bed of the primary tumor (best marked by clips)

CTVp_high = GTVp + 0.5cm (Indication according to AGO guidelines)
(Anatomically adjusted)

CTVn = Level 3-4 + IMC (Indication according to AGO guidelines). Level 1+2 in case of remaining macroscopic tumor and insufficient axillary surgery (see AGO guidelines)

In case of mastectomy:

CTVlow_chestwall (after mastectomy without reconstruction):

CTV definition regarding chest wall postmastectomy radiotherapy (standard arm only) in case of no reconstruction should follow the RTOG recommendations

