9.1 Randomization and stratification

Patients will be randomized to either the experimental arm or the standard of care arm in a 1:1 ratio, stratified by the following parameters:

- 1) biological subtype: Strata: Her2-type (HER2/neu positive), HR + type (no HER2/neu overexpression), triple negative
- 2) cN-Status (before start of NACT): Strata: cN+, cN-

- type of planned surgery: Strata: type of planned surgery: Strata: BCS vs Mastectomy (NSM, SSM or radical)

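### Section 6.4 requires internal mammary chain irradiation on tumour factors alone; the Section 6.4.3 table also requires initial cN+, so some experimental-arm cN0 patients get conflicting instructions

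*Protocol*

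**What the plan says.** Section 6.4 opens the radiotherapy instructions. On the experimental arm it first says "Regional lymph node radiotherapy may be indicated depending on initial findings before NACT". It then names central or medial location, ER/PR negativity, cT3 or cT4, cN2, inflammatory tumour and enlarged internal mammary nodes as conditions that "would necessitate internal mammary chain lymph node irradiation". The only exceptions given are left-sided cancer treated with trastuzumab (with or without pertuzumab) and relevant cardiac comorbidity.

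The experimental-arm table in Section 6.4.3 gives the indication by nodal region. Levels I to IV are treated if the patient was initially cN+. The internal mammary chain is treated if she was "cN+ and >=1 of the following factors", followed by the same seven factors. The same exceptions are footnoted. A note adds that pretherapeutic findings decide, whatever the response to systemic treatment.

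Section 6.4.6 includes the internal mammary chain in the experimental-arm nodal target volume with the words "IMC (if indicated according to protocol".

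**The concern.** Two sections give different rules for the same decision in the same arm. The wording in 6.4 is mandatory and concerns a radiation target volume, so a site that follows it will treat tissue that the indication table does not call for.

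The volume matters for dose. Section 6.4.11 allows the internal mammary target to be shortened caudally when heart or lung limits are not met, so the protocol itself regards it as driving those doses. Table 2 of that section also sets looser limits for plans with nodal irradiation including this chain. Without nodal irradiation, the left-sided mean heart dose limit is below 3 Gy; with it, below 6 Gy. For the ipsilateral lung, the mean dose limit moves from below 10 Gy to at most 14 Gy, and V20 from below 20% to at most 30%.

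There is a smaller consequence for compliance. Section 6.7 plans a retrospective quality check of all patients against the protocol. For the patients in conflict, either choice follows one section and departs from the other.

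**Working it through.** No published figure is in question, so the check compares the two rules as logical conditions and then asks who falls between them.

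**The rules.** Let F be at least one of the seven factors, N initial cN+, and X the shared exception.

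- Section 6.4: irradiate if F and not X.
- Section 6.4.3: irradiate if N and F and not X.

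They differ exactly when F is present, N is absent and X is absent.

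| Initial status | Factor present | Exception | 6.4 | 6.4.3 |
|---|---|---|---|---|
| cN+ | yes | no | irradiate | irradiate |
| cN+ or cN0 | yes | yes | no | no |
| cN0 | yes | no | **irradiate** | **not indicated** |

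**Which factors can occur with cN0.** Two of the seven are nodal findings: cN2, which is cN+ by definition, and enlarged internal mammary nodes, which would normally be staged cN+. That leaves 7 − 2 = 5: central or medial location, ER/PR negative, cT3, cT4 and inflammatory tumour.

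**Whether such patients are enrolled.** They are. Section 9.1 stratifies by nodal status before chemotherapy, with cN- as one level. Section 5.1 admits T2 to T4 tumours with no nodal condition, and admits "T1 a-c, if G3, triple negative, HER2- positive, or cN+/pN" positive disease, so a T1 triple-negative tumour qualifies without nodal involvement.

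**Where they sit in the stratification.**

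- All strata: 3 subtypes × 2 nodal levels × 2 surgery types = 12.
- cN- strata: 3 × 1 × 2 = 6.
- Triple-negative cN- strata: 1 × 1 × 2 = 2. Every patient here is ER/PR negative, and trastuzumab is not part of her treatment, so only cardiac comorbidity can remove her from the conflict.
- Remaining cN- strata: 6 − 2 = 4, affected only where one of the five factors is present and no exception applies.

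Strata are not patient shares. The nearest statement on numbers is in Section 4.6: "A small part of patients will have cT1/T2 cN0 M0 breast cancer with unfavorable biology". That covers cT1/T2 only; cT3/cT4 cN0 patients come on top. No count can be derived.

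**Whether another passage settles it.**

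- The lead-in sentence in 6.4 ties regional treatment to initial findings. These include tumour site and cT as well as nodal status, so it implies no cN+ condition.
- The wording in 6.4.6 refers back to the protocol, which contains both rules.
- Section 6.4.6 also covers cN0 patients found node-positive at surgery, describing them as those "who did not receive radiation to the axillary lymph node (ALN) region in the experimental arm". It names only the axillary region as untreated, so it leaves the internal mammary question open.
- No text gives 6.4.3 precedence over 6.4.

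**The case against.** The strongest reply is that 6.4 is an overview and 6.4.3 is plainly the rule. The opening paragraphs of 6.4 condense later subsections on timing, indication, technique and volumes. Section 6.4.3 carries the word indication in its title and sets out the decision region by region. An overview that repeats the table's seven factors in the table's order is naturally read as pointing to it.

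The rest of the protocol fits that reading. In 6.4.6 the experimental-arm nodal volume is built from levels 1 to 4 with the internal mammary chain added where indicated; no volume consisting of that chain alone is defined. Since levels I to IV are reserved for cN+ patients, the literal 6.4 rule would give a cN0 patient isolated internal mammary irradiation, which the planning section does not provide for. The recommendation of postoperative nodal radiotherapy for cN0 patients found node-positive at surgery also suggests that they normally receive no nodal fields beforehand.

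Finally, 6.4 refers sites to separate radiotherapy quality assurance guidelines, which are not at hand and may settle practice. Section 7 provides planning training and plan feedback from each site's first 10 patients, which could correct a systematic misreading.

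Most of this stands as evidence of intent: the 6.4 sentence has very probably lost its cN+ condition in summarising the table. It does not remove the conflict. The sentence is worded as a requirement, no precedence is stated, and the plan feedback is retrospective, so it may come after treatment.

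**Conclusion.** The concern holds. For an initially cN0 experimental-arm patient with any of five tumour factors and no exception, 6.4 requires internal mammary irradiation and 6.4.3 does not indicate it. In the 2 triple-negative cN- strata this applies to every patient without relevant cardiac comorbidity; in 4 further cN- strata it applies to some.

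The number of patients is unknown and may be small. The practical effect depends on which section sites follow and on what the quality assurance guidelines say. Sample size, power, alpha and endpoint definitions are unaffected. The point should be corrected because a stated treatment rule would lead to an unintended target volume if followed, assuming, as seems very likely, that the table is what was meant. The clinical leads have to confirm that assumption.

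**What to change.** In the 6.4 sentence on the internal mammary chain, add that it applies to initially cN+ patients. State in the same place that the 6.4.3 table is the sole indication rule for regional and internal mammary irradiation in the experimental arm. The clinical leads should confirm that this is the intended rule, and the radiotherapy quality assurance guidelines should be checked for the same condition.

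The cost is one phrase, one cross-reference and one document check. Design, sample size and analysis stay as they are.

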6.4.1 IOERT/IORT as boost irradiation

Intraoperative radiotherapy needs to be given according to the S3 or AGO guidelines.

Electrons with linear accelerator (IOERT 1x 10 Gy with electrons of adequate energy to cover the tumor bed) are for intraoperative Boost.

6.4.2 Whole Breast Radiotherapy (WBRT)

In the experimental arm, WBRT should preferably begin 2-4 weeks after the last application of NACT. In case of persistent toxicity that is regarded critical for radiotherapy, up to 6 weeks are allowed. Surgery should be performed after disappearance of the acute radiation induced erythema, preferably 3-6 weeks after completion of pre-operative radiotherapy. In the standard arm, post-operative WBRT should start 3-6 (up to 8) weeks after surgery.

6.4.3 Indication for breast/chest wall and regional lymph node irradiation:

Experimental arm (preoperative radiotherapy)

Preoperative radiotherapy Arm

- all patients receive whole breast radiotherapy (5x 2.7 Gy to 40.5 Gy +/- Boost RT)
- indication for regional lymph node radiotherapy depends on the initial findings before the start of the NACT +/ targeted therapy (5x 2.7 Gy to 40.5 Gy)

Lymph node region	indicated, if initially
Level I*- IV	cN+
Internal mammary chain LN**	cN+ and >=1 of the following factors

1) Central or medial tumor location

- 2) ER/PR negative tumor
- 3) cT3 tumor
- 4) cT4 tumor
- 5) cN2
- 6) inflammatory tumors
- 7) enlarged lymph nodes in the internal mammary chain

* Subtotal RT of Level I- II (see CTV definitions)

** No Internal mammary chain radiotherapy for left sided cancers treated with trastuzumab +/- pertuzumab and/or relevant cardiac comorbidity

Note: indications depend on the pretherapeutic findings irrespective of response to neoadjuvant systemic therapy

* Limited radiotherapy of Level I+II (see CTV definition)

** No IMC radiotherapy for left sided cancers treated in case of trastuzumab+/- pertuzumab or relevant cardiac comorbidity

Standard arm (postoperative radiotherapy):

The indication for whole breast / chest wall, for regional lymph nodes and boost radiotherapy should be administered according to the current recommendations of the AGO guideline.

6.4.4 Technical prerequisites

3D, IMRT, and VMAT-Planning have to be performed based on the individual CT-slices. Deep inspiration breath-hold techniques are strongly recommended in left-sided breast cancer. WBRT-treatment is delivered by photons 4-15 MV using linear accelerators. At least weekly verification imaging is required. Multileaf- and micro multi-leaf-collimators are required for proper treatment planning. Portal imaging or

cone beam CT are required for field verification. Photons (4-15 MV) and electrons (4-15 MeV) may be used.

6.4.5 Treatment technique

WBRT is usually performed using tangential wedged fields or IMRT/VMAT techniques with restricted angles to limit low-dose volumes in the lungs. IMRT and VMAT-techniques are preferred in case of regional lymph node irradiation, especially in internal mammary chain lymph node irradiation. In left-sided breast cancer, deep inspiration breath-hold is recommended if available at the study site.

In right-sided breast cancer, deep inspiration breath-hold is recommended in case of internal mammary chain lymph node irradiation.

The dose planning must follow the ICRU 50, 62 und 83.

